4.2 Analysis methods

4.2.1 Patient disposition

Patient disposition will be summarised using the all patients analysis set. The total number of patients will be summarised for the following groups: those who enrolled; and those who did not receive treatment after they have been enrolled (with reasons). The number and percentage of patients will be presented by the following categories: received treatment with study drug, entered OCS reduction phase, completed OCS reduction phase, entered maintenance phase, completed maintenance phase (defined as having attended EOT visit), completed maintenance phase and attended 3 dosing visits (not necessarily receiving IP) during maintenance phase, completed treatment with study drug, discontinued treatment (and reason), completed study and withdrawn from study (and reason). For DBL1, patients completed maintenance phase, completed maintenance phase and attended 3 dosing visits (not necessarily receiving IP) during maintenance phase, completed treatment with study drug, discontinued treatment, completed study and withdrawn from study will not be summarised. Instead, patients who discontinued treatment prior to the end of the OCS reduction phase and patients who withdrew from the study prior to the end of the OCS reduction phase will be summarised. Percentages will be based on the number of patients receiving treatment with the study drug. The same summary will also be presented for each subgroup defined in section 4.1 except the subgroups by patient's AI status at the end of the OCS reduction phase or at the end of maintenance phase.

The number of patients enrolled by region and by country and centre will be summarised for the FAS.

4.2.2 Demographics and patient characteristics

Demography data such as age, sex, race, and ethnicity will be summarised for all patients in the FAS and for each subgroup defined in section 4.1 except the subgroups by patient's AI

status at the end of OCS reduction phase or at the end of maintenance phase. Age will be derived from the date of informed consent-date of birth, rounded down to the nearest integer. For patients in countries where date of birth is not recorded the age as recorded in the eCRF will be used.

Descriptive statistics will be presented for the following demographic data (as per local regulations):

- Age
- Age group (≥ 18 -<50 years, ≥ 50 -<65 years or ≥ 65 years)
- Sex (Male, Female)
- Race (White, Black or African American, Asian, native Hawaiian or other Pacific islander, American Indian or Alaska native, Other)
- Ethnicity (Hispanic or Latino, Not Hispanic or Latino)

Descriptive statistics will be presented for the following baseline characteristics:

- Height (cm)
- Weight (kg)
- BMI (kg/m^2)
- BMI group (Normal: ≤ 25 , Overweight: $>25 - 30$, Obese: $>30-35$, Morbidly obese: >35)

In addition, BMI and BMI group will be summarized by age group and by region.

Various disease related baseline characteristics will also be summarised for all patients in the FAS and for each subgroup defined in section 4.1 except the subgroups by patient's AI status at the end of OCS reduction phase or at the end of maintenance phase. These include respiratory disease characteristics such as asthma duration, the number of exacerbations in the previous 12 months, and the number of exacerbations requiring hospitalizations in the previous 12 months.

The number and percentage of patients taking maintenance asthma medications at baseline will be summarized. Summary statistics will also be provided for ICS doses and OCS doses at baseline; ICS doses will be converted to their Fluticasone Propionate equivalent in micrograms and OCS doses will be converted to their Prednisolone equivalent in milligrams. The number and percentage of patients receiving OCS doses of >10 mg/day, >5 mg/day to ≤ 10 mg/day, and 5 mg/day will be presented. Duration of OCS treatment prior to study entry will be categorized as < 1 year and ≥ 1 year.

Medical and surgical histories will be summarised by MedDRA PT within MedDRA SOC in the full analysis set.

4.2.3 Prior and concomitant medications

A medication will be regarded as prior if it was stopped on or before the first IP dose date (i.e. medication stop date \leq first IP dose date).

A medication will be regarded as concomitant if the start date is after the first IP dose date, but prior to the end of treatment period, or if it started prior to the first IP dose date and was ongoing after the first IP dose date.

The number and percentage of patients who take prior medications, those who take allowed concomitant medications starting prior to first IP dose, those who take allowed concomitant medications starting after first IP dose, those who take disallowed concomitant medications starting prior to first IP dose, and those who take disallowed concomitant medications starting after first IP dose, will be presented for the FAS. Prior and concomitant medications will be classified according to the WHO Drug Dictionary (WHODD). The summary tables will present data by anatomical therapeutic chemical (ATC) classification category and preferred term (PT).

All prior and concomitant medications will be listed.

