2.2.1 Important protocol deviations

Important protocol deviations are a subset of protocol deviations that may significantly impact the completeness, accuracy, and/or reliability of the study data or that may significantly affect a subject's rights, safety, or well-being. Only important protocol deviations will be listed and tabulated in the CSR. Important protocol deviations will be reviewed and documented by the study physician and statistician prior to the study clean-file.

The following categories of protocol deviations will be reviewed by the study physician and statistician prior to database lock to determine those which are considered important deviations as outlined above.

- Patients who do not meet the inclusion criteria
- Patients who meet any of the exclusion criteria
- Concomitant use of disallowed medications (to be identified through programming)
- Patients who developed withdrawal criteria during the study but were not withdrawn

- Important deviation from OCS down-titration scheme or the monitoring of OCS down-titration.

More specifically, important protocol deviations (fully defined in section 4 of the study Non-Compliance Handling Plan (NCHP)) will include but are not limited to:

- Lack of peripheral blood eosinophil count of ≥ 150 cells/ μL assessed by central laboratory at Visit 1 or documented eosinophil count of ≥ 300 cells/ μL in the past 12 months
- Lack of documented chronic OCS therapy equivalent to a daily dose of 5mg of prednisone for at least 3 months directly preceding Visit 1
- Subject not on a stable dose of OCS for at least 4 weeks prior to Visit 1 or subject not switched to study-required prednisone/prednisolone as their oral corticosteroid for the duration of the study if on a different OCS medication
- Subjects who have a clinically important pulmonary disease other than asthma or ever been diagnosed with pulmonary or systemic disease, other than asthma, that are associated with elevated peripheral eosinophil counts
- Subject experiencing an asthma exacerbation requiring the use of systemic corticosteroids, increase in maintenance dose of OCS, or acute URTI/LRTI requiring antibiotics or antiviral medication within 30 days prior to Visit 2 (first dosing visit). (Note: An extension of the screening period up to 3 months is permitted to ensure full recovery of any exacerbation or acute infection)
- Subject who is concurrently enrolled in an interventional clinical trial

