8. APPENDIX

8.1 Partial dates for adverse events and prior/concomitant medication

Dates missing the day or both the day and month of the year will adhere to the following conventions in order to classify treatment-emergent AEs and to classify prior/concomitant medications:

Adverse Events

- The missing day of onset of an AE will be set to:
 - First day of the month that the event occurred, if the onset YYYY-MM is after the YYYY-MM of first study treatment
 - The day of the first study treatment, if the onset YYYY-MM is the same as YYYY-MM of the first study treatment
 - The date of informed consent, if the onset YYYY-MM is before the YYYY-MM of the first treatment.
- The missing day of resolution of an AE will be set to:
 - The last day of the month of the occurrence. If the patient died in the same month, then set the imputed date as the death date.

- If the onset date of an AE is missing both the day and month, the onset date will be set to:
 - January 1 of the year of onset, if the onset year is after the year of the first study treatment
 - The date of the first treatment, if the onset year is the same as the year of the first study treatment
 - The date of informed consent, if the onset year is before the year of the first treatment
- If the resolution date of an AE or end date of an IP is missing both the day and month, the date will be set to:
 - December 31 of the year of occurrence. If the patient died in the same year, then set the imputed date as the death date.

Prior/concomitant medication

- The missing day of start date of a therapy will be set to the first day of the month that the event occurred.
- The missing day of end date of a therapy will be set to the last day of the month of the occurrence.
- If the start date of a therapy is missing both the day and month, the onset date will be set to January 1 of the year of onset.
- If the end date of a therapy is missing both the day and month, the date will be set to December 31 of the year of occurrence.
- If the start date of a therapy is null and the end date is not a complete date then the start date will be set to the earlier of the imputed partial end date and the date of the first study visit.
- If the start date of a therapy is null and the end date is a complete date
 - and the end date is after the date of the first study visit then the start date will be set to the date of the first study visit.
 - otherwise the start date will be set to the end date of the therapy.

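### SAP 4.2.3 has no class for a medication started on the day of the first benralizumab dose: if continued it is neither prior nor concomitant, and if stopped the same day it counts as prior.

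*SAP*

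**What the plan says.** SAP 4.2.3 classifies medications by date relative to the first dose of investigational product (IP).

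- Prior: "A medication will be regarded as prior if it was stopped on or before the first IP dose date".
- Concomitant, first branch: "A medication will be regarded as concomitant if the start date is after the first IP dose date". The start must also fall earlier than treatment end.
- Concomitant, second branch: "or if it started prior to the first IP dose date and was ongoing after the first IP dose date".

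The section then sets up five groups for tabulation. One is prior medications. Two are for allowed concomitant medications, split by start before or after the first dose. The last two are "those who take disallowed concomitant medications starting prior to first IP dose, and those who take disallowed concomitant medications starting after first IP dose". No group is defined for a start on the day itself. The section closes with "All prior and concomitant medications will be listed".

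SAP 2.2.1 names this deviation category: "Concomitant use of disallowed medications (to be identified through programming"). It gives no date rule for that programming.

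Other parts of the SAP place the first-dose day inside the observation period. Section 3.3.3 includes adverse events with onset on that day, and section 3.3.2 starts the exacerbation period on that day.

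**The concern.** The two concomitant branches use strict inequalities on either side of the first dose date, and nothing covers equality. Every patient in the full analysis set has such a date. Protocol 4.2.1 and 7.2 put the first dose at Visit 2 and keep the patient under observation for 2 hours afterwards. Protocol 7.3 requires drugs for acute reactions to be at hand. A drug given in that window is on-treatment use, and the medication tables ought to show it as such.

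As written, the SAP could report a day-1 reaction as an on-study adverse event while showing the drug given for it as pre-treatment use, or not tabulating that drug at all. Several drug classes are also prohibited during the treatment period (protocol 7.8, Table 6), and that period begins at Visit 2. A disallowed drug started that day therefore belongs in the disallowed concomitant table, but the rules do not place it there.

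**Working it through.** No sample-size or precision figure is involved. The check is to apply the SAP 4.2.3 rules to every arrangement of dates around the first dose.

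**Inputs.** S = start date, E = stop date (later than everything else if ongoing), D = first IP dose date, T = end of the treatment period. The rules come from SAP 4.2.3.

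**Rules as written.**
- Prior: E ≤ D.
- Concomitant: (D < S < T) or (S < D and E > D).

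**Rules as proposed under the fix.**
- Prior: S < D and E ≤ D.
- Concomitant: (D ≤ S < T) or (S < D and E > D).

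| Start | Stop | As written | As proposed |
|---|---|---|---|
| before D | before D | prior | prior |
| before D | on D | prior | prior |
| before D | after D | concomitant | concomitant |
| on D | on D | **prior** | concomitant |
| on D | after D or ongoing | **neither** | concomitant |
| after D, before T | any | concomitant | concomitant |

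**The two rows that fail.**
- S = D and E > D: E ≤ D is false, so it is not prior. S > D is false and S < D is false, so neither concomitant branch applies. The record has no class.
- S = D and E = D: E ≤ D is true, so it is prior. Both concomitant branches are false for the same reason as above.

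A numerical enumeration with D = day 1 and an illustrative T = day 300 (an assumption; treatment length varies by patient) gave the same result. A day-1 start with a stop on day 2, 299, 300, 301 or ongoing was unclassified. A day-1 start with a day-1 stop was prior. A day-0 start with a day-2 stop, and a day-2 start, were concomitant.

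**Effect on the tables.** All five groups require a record to be either prior or concomitant, so the unclassified record appears in none of them. The same-day record appears once, under prior, and is missing from the allowed and disallowed concomitant groups.

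**Consistency with the rest of the SAP.** For an event on date D, SAP 3.3.2 and 3.3.3 both give on-study. For a drug started on date D, SAP 4.2.3 gives prior or no class.

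**Under the proposed rules** each record with S < T falls into exactly one class: S < D is split by E ≤ D against E > D, and D ≤ S < T is always concomitant. Only the two failing rows change.

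**The case against.** The strongest reply is that this is a boundary slip in a descriptive summary and that other provisions limit the harm. Much of that stands.

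- Adverse events and exacerbations on the first-dose day are still counted, so a reaction at Visit 2 is not lost from the safety tables.
- Changes in oral corticosteroid dose are recorded separately (protocol 5.1.1), and the primary endpoints in SAP 3.1 do not use this classification.
- Only drugs started on the first-dose day and continued leave the tables entirely. SAP 4.1 also promises patient-level listings in general terms, so such a record may still be listed.
- The protocol does not suggest many new starts at Visit 2: controller therapy and oral corticosteroid dose are to stay unchanged through induction.

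Two stronger readings are tempting.

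A reader might infer that disallowed drugs started on the first-dose day escape the deviation check, and so the sensitivity analysis that excludes important deviations. The documents do not show this. SAP 2.2.1 does not tie its programming to the 4.2.3 dates. It refers to protocol 7.8 and to the Non-Compliance Handling Plan, which is not among the documents, and it requires review by the study physician and statistician before lock. The sensitivity analysis in SAP 4.2.5.2 is itself optional. The loss is possible only if the 4.2.3 flag is reused.

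A reader might also see a second error in the partial-date rule of SAP 8.1: "The missing day of start date of a therapy will be set to the first day of the month that the event occurred". With the day unknown, this convention places some drugs begun after dosing before it. Moving them to the first dose date would do the reverse for drugs begun earlier that month. That is a choice between two imperfect conventions, not a mistake.

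None of this removes the gap in the 4.2.3 wording.

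**Conclusion.** The classification gap is real and follows from the wording of SAP 4.2.3 alone. A medication started on the first IP dose date has no class if continued and the wrong class if stopped that day, and both results conflict with how the SAP treats events on that day. The point is minor. It affects the prior and concomitant medication summaries and, only if the same flag drives it, the programmed disallowed-medication check.

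The number of affected records is unknown. The documents give no count or rate of medications started at Visit 2, so no estimate is offered, and the number could be zero. The conclusion assumes that the rules are programmed as written; a programmer who silently treated the day as on-treatment would avoid the problem but would depart from the SAP.

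**What to change.** In SAP 4.2.3:

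1. Define concomitant as started on or after the first IP dose date and before the end of the treatment period, or started before the first IP dose date and ongoing after it.
2. Define prior as started before the first IP dose date and stopped on or before it. A drug begun earlier and stopped on the first-dose day then stays prior, as now.
3. Relabel the two groups for later starts, allowed and disallowed, as *starting on or after first IP dose*. Without this step a day-1 start would become concomitant but still fit no column.

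In SAP 2.2.1, or in the deviation programming specification, state that the disallowed-medication check uses the same day-1 rule.

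The partial-date convention in SAP 8.1 can stay. A start imputed to the 1st of the month that coincides with the first dose date would then be classified rather than dropped.

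The cost is a few lines of SAP text and the matching table labels and programming. No new data are needed, and the primary analysis in the full analysis set does not change.

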4.2.4 Study treatment administration

Study treatment exposure and compliance will be calculated for the period to end of OCS reduction phase at DBL1, during maintenance phase, and the overall study period at DBL2.

Exposure to end of OCS reduction phase is calculated in days as (last dose of IP date - first dose of IP date + 1) if patient's last dose is prior to end of OCS reduction phase; or as (end of OCS reduction phase date - first dose of IP date + 1) otherwise.

Exposure during maintenance phase is calculated in days as (last dose of IP date - start date of maintenance phase + 1) if patient's last dose is after the end of OCS reduction phase; or 0 otherwise.

Duration of investigational product administration for the overall study period will be calculated in days as:

$$\text{Last dose date of IP} - \text{first dose date of IP} + 1$$

and will be summarised for all patients in FAS and for each subgroup defined in section 4.1 except the subgroups by patient's AI status at the end of OCS reduction phase or at the end of maintenance phase.

Study treatment compliance will be summarised for the full analysis set and calculated as:

$$\text{Study treatment compliance} = (\text{total doses administered} / \text{total doses expected}) \times 100.$$

Total number of doses expected will be calculated for the three study periods as defined for exposure. It includes all visits with protocol scheduled IP administration on or before a subject's IP discontinuation to end of OCS reduction phase or during maintenance phase, or treatment complete date (for the overall study period).

4.2.5 Primary outcome variables

All efficacy analyses will be conducted for all patients in the FAS and repeated by the subgroups defined in section 4.1 except the subgroups by patient's AI status at the end of OCS reduction phase or at the end of maintenance phase.

4.2.5.1 Primary analyses

For each of the primary endpoints and key supportive endpoints in Section 3.1, the data will be summarised using frequency counts and proportions. Proportions will be reported along with their two-sided 95% confidence interval, calculated using the Clopper-Pearson exact method.

The absolute and percent changes in OCS dose defined in section 3.1 will be summarised using descriptive statistics and displayed graphically.

For patients who do not achieve 100% reduction in their daily OCS dose, the starting OCS dose, the end OCS dose, the % reduction, and the reason for no further reduction will be listed. Baseline characteristics listed below will be summarized for patients who fail to reduce to 0 mg at the end of OCS reduction phase due to complete AI and those due to asthma exacerbation.

- Demographics: age, sex, race, height, weight, BMI, region
- Baseline and historical eosinophil count (category (<150, 150-<300, >=300) and summary statistics)
- Diagnosis of chronic rhinosinusitis without nasal polyps (CRS), or CRS with nasal polyps (CRSwNP)
- Past polypectomy (Y/N)
- Past sinus surgery (Y/N)
- Age at onset of Asthma (early vs. late onset (defined as <18 years / >=18 years) plus summary statistics for age)
- FeNO (historical)
- IgE and phadiatop (at screening)
- Baseline OCS dose per protocol cut-offs (<=5mg / >5-<=10mg / >10mg) and summary statistics
- Duration of chronic OCS use < or ≥ 1 year
- Number of prior exacerbations (categorised as 0, 1, 2, 3, 4+) and summary statistics
- Aspirin-triggered asthma (Y/N)
- GTI components at baseline

- HbA1c, LDL, SBP and DBP – summary statistics and categories as per GTI
- Steroid myopathy, skin toxicity, neuropsychiatric toxicity and infection – categories as per GTI
- Initial morning cortisol test result (as normal/partial/complete).

The statistical tabulation subgroups for the former summary will be normal/partial AI/complete AI by patient's AI status at the end of OCS dose reduction phase (see section 4.1). The statistical tabulation subgroups for the latter summary will be patients stopped down-titration due to 2+ asthma exacerbations and patients reached 0 mg OCS dose.

4.2.5.2 Sensitivity analysis

As a sensitivity analysis to the primary endpoint analysis, the primary efficacy outcome based on data as observed but excluding patients with any important protocol deviations related to efficacy (see section 2.2.1) may be analysed using the same method used for the primary analysis of the FAS.

As a second sensitivity analysis, the primary efficacy outcome based on data as observed but excluding patients who withdraw early from OCS reduction phase may be analysed using the same method used for the primary analysis of the FAS.

A sensitivity analysis to the first key supportive analysis will require patients with a baseline daily OCS dose of 5mg to achieve a final daily OCS dose of < 5mg unless the reason for no further reduction is complete AI.

4.2.6 Secondary outcome variables

4.2.6.1 OCS reduction

Absolute and percent change (where applicable) in OCS dose defined in section 3.2.1 will be summarised using descriptive statistics and displayed graphically. Absolute and percent changes will also be summarised by patient's AI status at the end of OCS reduction and at the end of maintenance phase (absolute changes only) (see section 4.1). Summary statistics for the OCS dose and absolute change in OCS dose at the end of the maintenance phase will be repeated excluding patients who withdraw from the study prior to the EOT visit, as a sensitivity analysis to address the objective of "sustained" reduction.

